6.5.1 Recurrence

- **Local failure** is defined as biopsy-proven recurrent breast cancer within 5 years from completion of radiation in the treated breast.
- **Nodal Failure** is defined as clinical evidence of recurrence by physical examination, CT or PET scan with or without biopsy proven disease in the regional axillary, supraclavicular, or internal mammary lymph nodes.
- **Distant failure** is defined as clinical evidence of recurrence by physical examination, CT or PET scan with or without biopsy proven disease beyond local or regional nodal sites.
- **Overall Survival** is defined as survival time between study registration until death or censored at date of last follow-up for patients still alive.

7 Statistical Plan

7.0 Statistical Plan

This is a study of accelerated partial breast irradiation (APBI) using proton therapy for patients with favorable Stage 0, I or II breast cancer. The trial will be conducted in two phases: first, a feasibility study and then, a phase II study. Since proton therapy is a new treatment modality at PENN, the first proton trial conducted in each cancer site (and here proton is prescribed on an accelerated treatment schedule) will be a feasibility study, in order to gain experience on both the logistics of proton planning, dosimetry, scheduling, and delivery, as well as patient safety issues.

7.1 Feasibility Study

7.1.1 Design

A total of 12 patients will be enrolled. The total dose of 38.5 CGE will be given in 10 fractions. The regimen is intended to be completed in 5 treatment days. A fractionation schedule of 3.85 Gy once a day for 10 fractions over 2-3 weeks is also permitted. Patients undergo 2 fractions per day, a minimum of 6 hours apart. Twelve patients will be enrolled and followed for a minimum of 30 days after the completion of radiotherapy to score acute toxicity. This shortened follow-up period is appropriate for an accelerated treatment schedule in which treatment may be completed in 5 days. Thirty days of observation from the end of radiotherapy will be required in all 12 patients prior to commencing the phase II study. Patients enrolled in the feasibility study will continue to be followed beyond 30 days post-radiation, since they contribute to primary and secondary endpoints of the phase II study.

CONFIDENTIAL

This material is the property of the University of Pennsylvania. Do not disclose or use except as authorized in writing by the study sponsor

7.1.2 Objectives.

The primary objectives are to determine feasibility and the acute toxicity profile of accelerated partial breast radiation using protons. Additional objectives, such as late toxicities, cosmesis, and clinical efficacy are evaluated in these patients on the phase II portion of the trial.

7.1.3 Endpoints

Primary Endpoints

Feasibility will be based on multiple radiation planning and treatment parameters. Should a patient experience one of the following events, treatment will be deemed infeasible:

- a) Patient cannot be given treatment because anatomy is such that a dosimetrically satisfactory treatment plan cannot be devised. For example, the dosimetry is unsatisfactory if < 95% of the target volume is covered by 95% of the dose.
- b) Patient is unable to tolerate more than 20% of treatments using proton radiotherapy (i.e., >2 of the 10 fractions). This can be for any reason, including the inability to set the patient up within acceptable limits of tolerance, or the patient is unable to tolerate treatment position or immobilization for duration of treatment. Thus, up to 20% (i.e., 2 of the 10 fractions) of treatments could be delivered using photons.
- c) Patient is unable to complete all treatment within 5 days of the estimated date of treatment completion or requires a treatment break of \geq than 5 days.
- d) No more than 20% of patients experience an acute toxicity, as defined below.

Acute toxicity is defined as any grade 3 or higher hematologic or non-hematologic toxicity, including skin changes, as graded by the NCI CTC Version 5.0, observed **within 30 days from the end of radiotherapy**, which is probably or definitely related to proton therapy.

Secondary Endpoints

Late toxicity is defined as any grade 3 or higher hematologic or non-hematologic toxicity which occurs more than 30 days after end of therapy. Late toxicities will be graded according to the CTC Version 5.0. Special attention will be paid to fibrosis and cosmesis. The time frame for late toxicity is open-ended because late toxicities have been known to occur a year or more after therapy. Follow-up for late toxicity will cease when a patient experiences disease progression since 2nd line therapies may then be initiated.

Cosmesis will be scored using the Harvard scoring system (scale = excellent, good, fair, poor) and CTC Version 5.0. In addition, cosmesis will be scored by the cosmesis and breast pain subscales of the Breast Cancer Treatment Outcomes Scale (BCTOS) instrument.

Clinical Efficacy. Time to local failure will be defined as the time from the start of radiation therapy to local failure. Overall survival will be defined from the time from the start of radiation therapy to death due to any cause or last patient follow-up. These outcomes will likely be summarized during the phase II study.

7.1.4 Rules for Early Termination for Feasibility and Acute Toxicity.

Bayesian probability calculations will be employed to define rules of early termination for feasibility and safety. The tables below indicate termination rules after groups of 3 patients have been treated, although the Bayesian probability of an event may be calculated at any time during the trial. Hundreds of patients

with certain types of cancer have undergone radiation therapy with protons. Thus, we will assume a modest amount of “prior” feasibility and safety data for proton for our Bayesian calculations.

Feasibility

We will assume a beta (5,1) prior, which is information equivalent to feasibility established in 5 of 6 treated patients. A feasibility rate $\geq 90\%$ is considered acceptable. If the number of patients in whom proton is deemed feasible is less than or equal to the number in the table below then termination will be considered as it is highly unlikely that the feasibility rate is $> 90\%$, as noted by the Bayesian posterior probabilities.

Bayesian Rule for Feasibility				
Patients treated	3	6	9	12
Patients in whom proton is feasible	1	4	6	9
Posterior Prob[feasibility rate $> 90\%$]	0.04	0.09	0.04	0.08
Action	Terminate enrollment			

Acute Toxicity

Acute toxicity with accelerated partial breast radiotherapy with photons is quite low, although skin toxicity is fairly common. Proton therapy is expected to spare normal tissues; therefore, a rate of Grade 3 or higher acute toxicity observed **within 30 days from the end of radiotherapy**, including skin changes, which is probably or definitely related to proton therapy of $\leq 20\%$ is considered acceptable. We will assume a beta (1,5) prior, which is information equivalent to Grade 3 or higher acute toxicity in one of 6 treated patients. If the number of patients with Grade 3 or higher acute toxicity is greater than or equal to the number in the table below, then termination will be considered, because it is likely that the toxicity rate is $> 20\%$, as noted by the Bayesian posterior probabilities.

Bayesian Rule for Acute Toxicity including skin changes				
Patients treated	3	6	9	12
Patients who experience acute toxicity	2	2	3	4
Posterior Prob [acute toxicity rate $> 20\%$]	0.80	0.62	0.70	0.76
Action	Terminate enrollment			

7.1.5 Statistical Analyses.

Feasibility: The posterior probability that this feasibility rate is 90% will be calculated. The feasibility rate and exact 90% CI will also be computed. The reasons why patients were not feasible will be tabulated.

Acute toxicity: All toxicities observed within 30 days from end of therapy will be graded by CTC Version 5.0 and tabulated. The posterior probability that this acute toxicity rate is 20% will be calculated.

Late toxicity: All toxicities observed later than 30 days from end of therapy will be graded by the CTC Version 5.0 and tabulated.

Cosmesis will be scored using the Harvard scoring system and CTC Version 5.0. BCTOS will be scored every 6 months and fold changes over time will be described and plotted.

Clinical efficacy: Local control (time to local failure) and overall survival will be estimated by the Kaplan-Meier method. It is likely that these time-to-event outcomes will be summarized after completion of the phase II study.

Estimation of Event Rates: The table below displays the 90% exact binomial confidence intervals based on 12 patients treated.

No. of Events	%	90% exact CI	No. of Events	%	90% exact CI
0	0.0	17.5*	7	58.3	31.5 , 81.9
1	8.3	.43 , 33.9	8	66.7	39.1 , 87.7
2	16.7	3.0 , 43.8	9	75.0	47.2 , 92.8
3	25.0	7.2 , 52.7	10	83.3	56.1 , 97.0
4	33.3	12.3 , 60.9	11	91.7	66.1 , 99.6
5	41.7	18.1 , 68.5	12	100.0	82.5*
6	50.0	24.5 , 75.5			* 90% 1-sided CI

7.2 PHASE II STUDY.

7.2.1 Design and Objectives.

Once feasibility and safety are established, then the phase II portion of the study will commence. A total of 57 patients will be enrolled; 12 patients are included from the feasibility study and 45 additional patients are enrolled in the phase II study. The two primary objectives are: to determine whether the rate of Grade 3+ acute toxicity is $\leq 20\%$ and whether the rate of maintained excellent to good cosmesis is $\geq 85\%$ at 2 years post-XRT. Only patients with excellent or good cosmesis at baseline contribute to this analysis.

7.2.2 Endpoints.

Acute Toxicity, as defined in Section 7.1.3

Cosmesis, as scored by the Harvard scale, CTC Version 5.0 and BCTOS scoring systems.

Late Toxicity, Local control and overall survival, as defined in Section 7.1.3

7.2.3 Rules for Early Termination for Acute Toxicity.

A primary objective is to assess the rate of acute toxicity which will be tested by chi-square test at the end of the phase II study. But since accelerated partial breast radiotherapy with photons is a novel intensive treatment course, we have decided to continue Bayesian monitoring of acute toxicity throughout the course of the phase II study. Assuming a beta (1,5) prior, if the number of patients with Grade 3 or higher acute toxicity is greater than or equal to the number in the table below, then termination will be considered, because it is likely that the toxicity rate is $>20\%$, as noted by the Bayesian posterior probabilities.

Bayesian Rule for Acute Toxicity including skin changes				
Patients treated	20	30	40	50
Patients who experience acute toxicity	6	8	10	12
Posterior Prob [acute toxicity rate $>20\%$]	0.89	0.85	0.82	0.79
Action	Terminate enrollment			

CONFIDENTIAL

This material is the property of the University of Pennsylvania. Do not disclose or use except as authorized in writing by the study sponsor

7.2.4 Statistical Analyses.

The following are standard methods for data analysis which will be employed. Graphical analyses will include scatter plots, box plots, mean (\pm SE) plots and histograms. The distribution of continuous variables will be characterized with mean, median, standard deviation and range, while the distribution of categorical variables will be described with frequency, percentage and 95% CI. Toxicities will be categorized as acute or late and will be graded and tabled by toxicity type. The Grade 3+ acute toxicity rate and confidence interval will be calculated and a one sample chi-square test will be performed. The rate of excellent to good cosmesis at 2 years post-XRT and confidence interval will be calculated and a one sample chi-square test will be performed. Time to local failure and overall survival will be estimated by the Kaplan-Meier method.

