4.4 Dose fractionation and specification

4.4.1 A total dose of 38.5 Gy (RBE) will be prescribed to the ICRU reference point (usually isocenter). Two fractions, each of 3.85 GY (RBE) separated by at least 6 hours, will be administered on 5 treatment days (over a period of 5 to 10 days) for a total of 10 fractions. A fractionation schedule of 3.85 Gy once a day for 10 fractions over 2-3 weeks is also permitted.

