4.6 Treatment Duration

Proton radiation therapy will, in most instances, be completed within 2 weeks of the start of treatment. This may be extended if subjects require a break from treatment. Criteria for break would include any **Grade 3 or Grade 4** toxicity. All subjects experiencing **Grade 4** toxicity will be taken off study. Further treatment plans will be decided at the discretion of their treating physician.

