4.7 External Beam Equipment and Beam Delivery

Protons: A 230 MeV proton beam will be used. Treatments will be administered in the Roberts Proton Therapy Center at the University of Pennsylvania. All charged particle treatment will be given with the patient in the appropriate immobilization device and aligned based on the departmental protocol.

Film or digital images will be taken prior to the initial treatment to verify the position of the patient and the aperture and as appropriate. A radiation oncologist will check the first film on all fields. A radiation therapist will check subsequent films taken before treatment.

All set-up films will be permanently filed for each subject.

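### Up to 2 of 10 fractions may be photons in a patient scored feasible, but the acute-toxicity endpoint counts only proton-related events and Section 4 does not mention photons

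*Combined protocol and SAP*

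**What the plan says.** **Delivery (Section 4).** Section 4.4 sets the dose: "A total dose of 38.5 Gy (RBE) will be prescribed to the ICRU reference point (usually isocenter"), in 10 fractions of 3.85 Gy (RBE). Section 4.6 gives the duration for protons: "Proton radiation therapy will, in most instances, be completed within 2 weeks of the start of treatment". Section 4.7 gives the equipment: "Protons: A 230 MeV proton beam will be used". Nothing in Section 4 mentions a photon fraction, and nothing in it forbids one.

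**Feasibility (7.1.3, item b).** A patient is infeasible if "Patient is unable to tolerate more than 20% of treatments using proton radiotherapy (i.e., >2 of the 10 fractions"). The item then draws the consequence: "Thus, up to 20% (i.e., 2 of the 10 fractions) of treatments could be delivered using photons". A patient with one or two photon fractions who meets no other criterion is therefore feasible. Section 7.1.5 tabulates the reasons for infeasibility only.

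**Acute toxicity (7.1.3, 7.1.4, 7.2).** The endpoint is Grade 3 or higher toxicity within 30 days of the end of radiotherapy "which is probably or definitely related to proton therapy". Section 7.1.4 repeats that attribution for the feasibility-stage stopping table. Section 7.2.2 carries the definition into phase II: "Acute Toxicity, as defined in Section 7.1.3". Under 7.3 all 57 patients contribute to the test, with no provision for patients who had photon fractions.

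**The concern.** There are two separate matters.

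The first is consistency. The only statement that photons may form part of treatment sits in an endpoint definition in the statistical section. A reader of Section 4 alone would not know of it.

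The second is the match between numerator and denominator. A mixed-course patient is in the toxicity denominator, but her event enters the numerator only if the investigator judges it probably or definitely due to protons. No rule says how to attribute an event after a mixed course. Section 8.1 asks the investigator to weigh concomitant therapy as an alternative cause, and a photon fraction could be read that way. At stake are a primary endpoint and a safety stopping rule with small counts, in a single-arm trial with no comparator to absorb an undercount.

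**Working it through.** **1. Size of the tolerance.** Inputs from 4.4 and 7.1.3(b): 2 fractions of 3.85 Gy out of 38.5 Gy. 2 × 3.85 = 7.7 Gy, and 7.7 / 38.5 = 20%, as the plan states. A feasible mixed-course patient has thus had at least 8 of 10 fractions as protons.

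**2. The feasibility-stage toxicity table (7.1.4).** With a beta(1,5) prior and x events in n patients, the posterior is Beta(1 + x, 5 + n − x). The table gives P(rate > 20%). The plan's figures reproduce. The last column shows the posterior if one event at the boundary is not counted.

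| Patients | Boundary (events) | Plan | Recomputed | One event fewer |
|---|---|---|---|---|
| 3 | 2 | 0.80 | 0.797 | 0.503 |
| 6 | 2 | 0.62 | 0.617 | 0.322 |
| 9 | 3 | 0.70 | 0.698 | 0.448 |
| 12 | 4 | 0.76 | 0.758 | 0.549 |

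The rule acts on whole counts, so one uncounted event means the boundary is not met. The same holds for the phase II counts in 7.2.3 (6, 8, 10 and 12 events at 20, 30, 40 and 50 patients).

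**3. The final toxicity test (7.3).** Inputs: n = 57, null 35%, alternative 20%, one-sided 10%.

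- Standard error under the null: √(0.35 × 0.65 / 57) = 0.0632. Under the alternative: √(0.20 × 0.80 / 57) = 0.0530.
- Power = Φ[(0.15 − 1.2816 × 0.0632) / 0.0530] = Φ(1.303) = 0.904, which agrees with the stated 90%.
- The null is rejected when the count is at most 57 × (0.35 − 1.2816 × 0.0632) = 15.3, that is, at 15 or fewer events. The exact probability of this at a true rate of 35% is 0.107.

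**4. Illustration of event loss.** The documents give neither the frequency of photon substitution nor the chance that an event would be attributed to it. Assume that a share m of all radiotherapy-related Grade 3 or higher events goes uncounted. The counted rate is then 0.35 × (1 − m), and the expected number lost is 57 × 0.35 × m.

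| Assumed m | Counted rate | Expected events lost | P(15 or fewer of 57) |
|---|---|---|---|
| 0% | 35.0% | 0 | 0.107 |
| 2% | 34.3% | 0.4 | 0.128 |
| 5% | 33.25% | 1.0 | 0.166 |
| 10% | 31.5% | 2.0 | 0.245 |

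Here m is the share of events arising in mixed-course patients times the share of those attributed to photons. For example, 5% needs 10% of events in mixed-course patients and half of these attributed to photons (0.10 × 0.50 = 0.05). If substitution is rare, m is close to 0.

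**5. Feasibility reporting.** A patient with two photon fractions and a patient with none both score as feasible, and 7.1.5 tabulates only the infeasible. As a ceiling and not a forecast, 12 × 2 = 24 of 120 fractions could be photons with a 12 of 12 feasibility result. No planned table would show it.

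**The case against.** **Silence is not contradiction.** Section 4 can be read as the planned treatment and 7.1.3(b) as the tolerated departure from it. Sections 4.5.4 and 4.7 also refer to a departmental protocol that is not part of these documents. This stands. A reader might infer that Section 4 prohibits photons; it does not.

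**The threshold is deliberate.** Feasibility is defined as tolerating at least 8 of 10 proton fractions, so scoring these patients as feasible is intended. This also stands. A reader might infer that the 20% allowance is a mistake or makes the feasibility result invalid; the text does not support that.

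**The loss of events is not shown.** An event drops out only if the investigator judges it not even probably related to a modality that gave at least 80% of the fractions. Section 7.1.4 calls acute toxicity with photon partial-breast treatment quite low, though with skin toxicity fairly common. Section 1.7 reports higher skin doses with protons than with photons in one earlier trial, so investigators have little reason to blame the photon fractions. Section 7.1.5 tabulates all toxicities within 30 days, and 8.3.3 sends every Grade 3 or higher event to the safety committee. These points make a large loss unlikely and keep events visible. They do not change what the primary endpoint and the stopping rules count.

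**Dosimetry.** A reader might infer that the normal-tissue limits in 4.5.3 would be checked on a plan other than the one delivered. The documents do not say that a photon fraction would go unplanned or unsummed, and those limits are percentages of prescribed dose not tied to modality.

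**Conclusion.** The point holds as a wording gap with a simple remedy. Sections 4 and 7.1.3(b) need to be reconciled on whether and how photon fractions belong to protocol treatment. The attribution rule should match the denominator: as written, the toxicity rate can lose events in mixed-course patients and cannot gain any, so the only possible error is downward. That the rate is in fact biased downward is a stronger inference, and the documents do not support it. The frequency of substitution is unknown, and so is the investigators' attribution practice.

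The firm result is that a single uncounted event decides whether a stopping boundary is met. The rise in the chance of accepting a 35% rate, from 0.107 to between 0.128 and 0.245, rests entirely on the assumed 2% to 10% loss; the true loss may be close to zero. The sample size and the stated power are unaffected.

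**What to change.** 1. Reconcile Section 4 with 7.1.3(b), so that one statement governs whether photon fractions are part of protocol treatment. The clinical choice is the sponsor's.
2. In 7.1.3 and 7.1.4, change the attribution from proton therapy to *related to the protocol radiotherapy course (any modality)*. Section 7.2 inherits the change through 7.2.2.
3. Keep all treated patients in the primary toxicity and cosmesis analyses. Do not restrict those analyses to all-proton patients: that would select on set-up or tolerance problems arising during treatment and could flatter the results.
4. Report the number of photon fractions per patient beside the feasibility rate, and give the count of feasible patients treated entirely with protons as a descriptive supplement. The feasibility definition stays as it is.

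The cost is a short wording amendment and one descriptive table drawn from treatment records. An event truly caused by a photon fraction would now count against the regimen. That is the cautious direction for a safety rule, and it matches a denominator that already includes the patient.

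### Feasibility item (d) in 7.1.3 is a cohort rate, worded as the acceptable result, in a list of per-patient failure events, so it cannot enter the feasible count

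*Combined protocol and SAP*

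**What the plan says.** Section 7.1.3 introduces the feasibility endpoint with "Feasibility will be based on multiple radiation planning and treatment parameters" and then gives the rule: "Should a patient experience one of the following events, treatment will be deemed infeasible". Items (a) to (c) follow that form. Each describes something that happens to one patient: no satisfactory plan, too many fractions not tolerated on protons, or late completion or a long break. Item (d) is "No more than 20% of patients experience an acute toxicity, as defined below".

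The rules that use this endpoint count patients. The feasibility rule in 7.1.4 applies "If the number of patients in whom proton is deemed feasible is less than or equal to the number in the table below", and 7.1.5 asks for a feasibility rate with an exact 90% interval and adds "The reasons why patients were not feasible will be tabulated".

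Elsewhere toxicity is kept apart from feasibility. Section 7.0 gives the purpose of the first stage as "in order to gain experience on both the logistics of proton planning, dosimetry, scheduling, and delivery, as well as patient safety issues". Section 7.1.2 states "The primary objectives are to determine feasibility and the acute toxicity profile of accelerated partial breast radiation using protons". In 7.1.4 toxicity has its own prior, its own limit (20% or less is acceptable) and its own table, which is triggered when "the number of patients with Grade 3 or higher acute toxicity is greater than or equal to the number in the table below". Section 7.2.1 makes phase II depend on feasibility and safety, named as two things.

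**The concern.** Item (d) has two faults. Its direction is reversed: the list defines failure, but (d) describes the outcome that 7.1.4 accepts. Its unit is also wrong, because a single patient cannot experience a cohort proportion. The feasible or not feasible status that 7.1.4 and 7.1.5 need for each patient therefore cannot take (d) as an input.

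Feasibility is a primary endpoint of the first stage. It feeds a termination table, a reported rate with its interval, a posterior probability and a table of reasons. Two analysts could handle (d) differently and report different feasibility rates from the same 12 patients. In one realistic case they would also disagree on whether a boundary had been met before phase II.

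**Working it through.** **Inputs.** From 7.1.4:
- Feasibility: prior beta(5,1), limit 90%. The boundary is met at 1, 4, 6 or 9 or fewer feasible patients of 3, 6, 9 and 12, that is, at 2, 2, 3 or 3 or more infeasible patients.
- Acute toxicity: prior beta(1,5), limit 20%. The boundary is met at 2, 2, 3 or 4 or more toxic patients.

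**1. The plan's own figures.** With x of n patients, the feasibility posterior is P(p > 0.90) under Beta(5 + x, 1 + n − x). The toxicity posterior is P(p > 0.20) under Beta(1 + x, 5 + n − x).
- Feasibility at 1/3, 4/6, 6/9, 9/12: 0.038, 0.090, 0.044, 0.083 (printed 0.04, 0.09, 0.04, 0.08).
- Toxicity at 2/3, 2/6, 3/9, 4/12: 0.797, 0.617, 0.698, 0.758 (printed 0.80, 0.62, 0.70, 0.76).

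All eight reproduce. The tables in 7.1.4 are sound; the fault lies in the definition that feeds one of them.

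**2. Item (d) read literally.** It is satisfied by 0, 1 or 2 toxic patients of 12 (0%, 8.3%, 16.7%) and not by 3 (25%). At a true rate of 10%, P(2 or fewer of 12) = 0.282 + 0.377 + 0.230 = 0.89. A literal reading would usually label a low-toxicity treatment infeasible.

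**3. Worked case: 3 toxicities in 12, no (a) to (c) events.**

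| | Toxic patients counted as infeasible | Not counted |
|---|---|---|
| Feasible | 9/12 (90% CI 47.2 to 92.8, table in 7.1.5) | 12/12 |
| P(feasibility > 90%) | Beta(14,4): 0.08 | Beta(17,1): 1 − 0.9^17 = 0.83 |
| Feasibility boundary (9 or fewer) | met | not met |
| P(toxicity > 20%) | Beta(4,14): 0.55 | 0.55 |
| Toxicity boundary (4 or more) | not met | not met |

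**4. Chance of meeting a boundary within 12 patients, no (a) to (c) failures.** Write p for the true toxicity rate and q = 1 − p.
- Not counted: only the toxicity table can be met. No boundary is met if there is at most 1 toxicity by 6 patients, at most 2 by 9 and at most 3 by 12.
- Counted: the joint boundary is 2, 2, 3, 3, so the last condition becomes at most 2 by 12.

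The numbers of admissible sequences with 0, 1, 2 and 3 toxicities in 12 are 1, 12, 51 and 91. For 51: 15 with none in the first six patients, plus 6 × 6 with one. For 91: 19 with none in the first six, plus 6 × 12 with one.
- P(no boundary, counted) = q^12 + 12pq^11 + 51p²q^10
- P(no boundary, not counted) = the same + 91p³q^9

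| True toxicity | Not counted | Counted | Gap = 91p³q^9 |
|---|---|---|---|
| 5% | 0.035 | 0.042 | 0.007 |
| 10% | 0.128 | 0.163 | 0.035 |
| 20% | 0.408 | 0.506 | 0.098 |

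At 10%, for example: 0.2824 + 0.3766 + 0.1778 = 0.8368, so counted is 0.163. Adding 0.0353 gives 0.8721, so not counted is 0.128. The whole gap comes from reaching 12 patients with exactly 3 toxicities.

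**5. Reversing the sign only.** As an observed proportion, more than 20% of patients is reached at 1/3 (33%), 2/9 (22%) and 3/12 (25%). The toxicity boundaries there are 2, 3 and 4. The toxicity posteriors at 1/3, 2/9 and 3/12 are 0.50, 0.45 and 0.55, against 0.80, 0.70 and 0.76 at the printed boundaries. At 6 patients both rules need 2.

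**6. Counting toxicity per patient.** A true toxicity rate of 20%, which 7.1.4 accepts, would hold feasibility to at most 100% − 20% = 80%, below the 90% that 7.1.4 requires.

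**The case against.** The strongest reply is that the intent can be recovered. Section 7.1.4 gives the direction, the limit and a separate table for toxicity, and 7.0, 7.1.2 and 7.2.1 treat safety as distinct from feasibility. A sensible analyst would score (a) to (c), run the two tables side by side, and never apply (d) literally. This largely stands. It does not remove the defect, because (d) remains in the feasibility list and no section says how it is to be handled.

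The reply is also right that the effect is narrow. Without (a) to (c) failures, the two readings differ only at the final look with exactly 3 toxicities, when all 12 patients are already enrolled. The text of 7.1.4 says that meeting a boundary leads to termination being considered, although the action row of the tables is worded more firmly. Some toxicities may already count under (c) through a treatment break. If an assumed share s of them did so independently, the gap would shrink by the factor 1 − s³: at 10% toxicity it is 0.035, 0.031 and 0 for s of 0, 0.5 and 1.

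A reader might infer that the whole feasibility endpoint cannot be scored, or that the trial would in practice reject a safe treatment. The documents support neither: (a) to (c) can be scored, the printed posteriors are correct, and 7.1.4 fixes the direction for toxicity. Nor is the phase II toxicity test affected, since it uses the acute toxicity definition and not the feasible count.

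**Conclusion.** Item (d) is wrong as written, in both unit and direction, and the plan does not say how it enters the feasible count. That conclusion rests on the text alone and is firm. The plan as a whole favours treating acute toxicity as a separate trial-level criterion.

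The consequence is moderate. For 3 toxicities in 12, the reported feasibility is 75% or 100% and a boundary is or is not met, depending on the reading. The chance of meeting a boundary differs by 0.7, 3.5 and 9.8 percentage points at true toxicity of 5%, 10% and 20%. These figures assume no (a) to (c) failures, looks at 3, 6, 9 and 12 patients, and both tables in force. The documents give no rate for (a) to (c) failures. Independent failures of that kind would widen the gap, but the conclusion does not rely on them. The point should be corrected; it does not undermine the trial.

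**What to change.** Reconcile 7.1.3 with 7.1.4 in a short amendment. The reading that best fits the rest of the plan is to:
- remove (d) from the infeasibility list and score feasibility per patient on (a) to (c);
- state that acute toxicity is a separate trial-level criterion, assessed by the Bayesian toxicity rule in 7.1.4 and the posterior in 7.1.5. The sentence should not confine the assessment to the printed table, because 7.1.4 allows the probability to be calculated at any time.

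If the sponsor does intend toxicity to count as infeasibility, (d) should be reworded as an event in the individual patient, and the 20% toxicity limit reconciled with the 90% feasibility limit.

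Reversing the sign of (d) is not a sufficient repair, because the resulting rule would disagree with the toxicity boundaries at 3, 9 and 12 patients.

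The cost is a line or two in 7.1.3 and the IRB submission that section 11 requires for any amendment. No added data collection or patients are needed.

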8.4 Stopping Rules

See section 7.2

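### Text and tables in 7.1.4 and 7.2.3 disagree on whether a crossed early-termination limit stops enrolment, and 8.4 omits 7.1.4; the 90% power in 7.3 holds only if no limit stops the trial

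*Combined protocol and SAP*

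**What the plan says.** Section 7.1.4 sets limits for feasibility and for acute toxicity: "The tables below indicate termination rules after groups of 3 patients have been treated", that is, at 3, 6, 9 and 12 patients. It adds that "the Bayesian probability of an event may be calculated at any time during the trial". Section 7.2.3 continues the toxicity monitoring at 20, 30, 40 and 50 patients.

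- **Text, toxicity (7.1.4, repeated in 7.2.3):** "then termination will be considered, because it is likely that the toxicity rate is" above 20%.
- **Text, feasibility (7.1.4):** if the number of feasible patients "is less than or equal to the number in the table below then termination will be considered as it is highly unlikely" (what is unlikely being a rate above 90%).
- **Action row of all three tables:** "Terminate enrollment".
- **Section 8.4, Stopping Rules, in full:** "See section 7.2".

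Section 7.3 claims 90% power with 57 patients for a one-sided 10% chi-square test of an acute toxicity rate of 35% or more against 20% or less. It does not mention the early-termination limits.

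**The concern.** The text makes a crossed limit a prompt for a decision, while the Action row makes it an instruction. Both apply to the same counts. No other section says which prevails, or which person or committee decides. Section 8.5.1 treats departures from stopping rules as deviations needing IRB approval and DSMC review, so whether enrolling past a limit is a deviation also depends on the reading.

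The cross-reference in 8.4 makes this harder to resolve, because a reader who starts there is not sent to the first four toxicity limits or to any feasibility limit.

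Two things are at stake: how many patients are exposed if toxicity is unacceptable, and whether the power statement in 7.3 describes the trial that will be run.

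**Working it through.** **Inputs.** Toxicity limits, as the number of patients with toxicity that meets the limit over patients treated: 2/3, 2/6, 3/9, 4/12 (7.1.4) and 6/20, 8/30, 10/40, 12/50 (7.2.3). The phase II counts must be cumulative from the first feasibility patient, since 50 exceeds the 45 patients added. From 7.3: N = 57, null 35%, alternative 20%, one-sided 10%.

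**1. The plan's posteriors.** For toxicity, P(p > 0.20) under Beta(1 + x, 5 + n − x) gives 0.797, 0.617, 0.698 and 0.758 at the 7.1.4 limits (stated 0.80, 0.62, 0.70, 0.76). For feasibility, P(p > 0.90) under Beta(5 + x, 1 + n − x) gives 0.038, 0.090, 0.044 and 0.083 (stated 0.04, 0.09, 0.04, 0.08). Both sets reproduce.

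The 7.2.3 posteriors do not reproduce with the stated beta(1,5) prior (0.780, 0.745, 0.720, 0.702 against 0.89, 0.85, 0.82, 0.79). They match beta(1,1). That is a separate matter and does not affect what follows, which uses only the tabulated counts.

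**2. The plan's power, with no stopping.** Normal approximation:

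z = [(0.35 − 0.20)√57 − 1.2816√(0.35 × 0.65)] / √(0.20 × 0.80) = (1.1325 − 0.6113) / 0.4 = 1.303, so power = 0.904.

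In whole patients the test rejects at 15 or fewer of 57 (z = −1.375 at 15, −1.097 at 16, critical value −1.282). Exact power is P(X ≤ 15 | 0.20) = 0.909, and exact type I error is P(X ≤ 15 | 0.35) = 0.107. The stated 90% reproduces, with no limit applied.

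**3. The same test with all eight toxicity limits binding.** Let a_k(s) be the probability of reaching look k with s events and no earlier limit met:

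a_k(s) = Σ_{r < x_{k−1}} a_{k−1}(r) · Bin(s − r; n_k − n_{k−1}, p)

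- P(stop at look k) = Σ_{s ≥ x_k} a_k(s)
- Expected enrolment = Σ n_k · P(stop at k) + 57 · P(no stop)
- P(complete and reject) = Σ_{s < 12} a_8(s) · P(Bin(7, p) ≤ 15 − s)

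First look at p = 0.20: 3(0.04)(0.80) + 0.008 = 0.104. The full recursion gives these stopping probabilities:

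| True rate | 3 | 6 | 9 | 12 | 20 | 30 | 40 | 50 | Total |
|---|---|---|---|---|---|---|---|---|---|
| 20% | 0.104 | 0.241 | 0.043 | 0.021 | 0.034 | 0.045 | 0.038 | 0.032 | 0.558 |
| 35% | 0.282 | 0.399 | 0.072 | 0.040 | 0.075 | 0.067 | 0.034 | 0.016 | 0.984 |

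**4. The two readings compared.**

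| | All eight bind | None stops the trial |
|---|---|---|
| Expected enrolment, true 35% | 10.9 | 57 |
| Expected enrolment, true 20% | 32.8 | 57 |
| Stopped by patient 12, true 35% | 0.79 | 0 |
| Stopped by patient 12, true 20% | 0.41 | 0 |
| Stopped early in all, true 20% | 0.56 | 0 |
| Complete and reject, true 20% (power) | 0.44 | 0.91 |
| Complete and reject, true 35% (type I error) | 0.015 | 0.107 |

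**The case against.** The best defence is that advisory limits are a legitimate choice and that the trial is not unsupervised. Section 8.3.3 sends every grade 3 or higher event to the DSMC within ten days, and 8.5.1 has that committee review safety reports monthly and make recommendations. This stands as far as it goes. It does not say whether the limits bind, and none of it is tied to the tables. It does make the column in which nothing stops the trial an outer bound, since it assumes that oversight never acts.

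Three stronger readings are tempting and should not be drawn:

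- **That 8.4 leaves the trial without a toxicity limit before patient 20.** The cross-reference is incomplete, but it repeals nothing. Section 7.1.4 sets looks from the third patient, and 7.2.3 describes its own monitoring as a continuation. Section 7.2.1 opens phase II only once feasibility and safety are established, and 7.1.1 requires 30 days of observation in all 12 patients first.
- **That a crossed limit requires no action.** Even the softer text requires termination to be considered, and the DSMC reporting applies regardless.
- **That the limits ought to bind, or that enrolment must be suspended at each crossing.** Neither text nor table contains a suspension rule. With these limits, 56% of trials at the acceptable 20% rate would meet one, and 13% would at a true 10% rate. Whether to make the limits binding is the sponsor's decision.

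**Conclusion.** The point stands in this form: text and Action rows give conflicting rules for the same limits in both stages, nothing else in the protocol settles the conflict, and 8.4 omits one of the two sections that hold the rules.

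The conflict is more than editorial, because binding limits and 90% power cannot both hold. If all toxicity limits bind, power at a true 20% rate is 0.44 and type I error at 35% is 0.015. If none stops the trial, the figures are 0.91 and 0.107. Advisory limits that are sometimes acted on would fall between these.

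The figures assume independent patients, looks exactly at the tabulated numbers and complete 30-day data at each look; the protocol requires that wait only before phase II. They cover the toxicity limits only. Binding feasibility limits could only add to early stopping.

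**What to change.** Reconcile the text and Action rows of 7.1.4 and 7.2.3 to one rule that says whether meeting a limit ends enrolment or triggers a decision, and which body decides. Make 8.4 cite both 7.1.4 and 7.2.3. State in 7.3 the power and type I error for the reading chosen.

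The cost is a few wording changes and one calculation in an amendment, with no added patients. There is a downside either way. If the limits bind, 7.3 must report power far below 90% for these limits. If they are advisory, the Action rows must be reworded, and the power figure should be described as holding only when no limit leads to a stop.
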